Data will be reported quantitatively. All analyses will be performed from the intention-to-treat principle. Missing data on background variables will be dealt with by multiple imputation. Final data analysis will begin when the last participant in the multicentric RCT has completed the follow-up period. The primary endpoint, work absenteeism due to illness, will be reported as the total number of sick days with standard deviation. Total days of absenteeism will be analysed using a Bayesian negative binomial regression with a fixed effect for BCG, hospital, professional category, age, enrolment week and number of average workdays per week. The brm function from the R package "brms" will be used for fitting the negative binomial model. The effect will be reported as a relative risk with 95% confidence interval (CI). Please refer to section interim analysis for type-1 error control and power.

Similar regression models will be used for secondary endpoints. Cumulative incidence outcomes will primarily be analysed using Cox Proportional Hazard Regression.

Continuous baseline characteristics will be reported as means with the standard deviation or medians with the inter-quartile range, as appropriate. Categorical baseline characteristics will be reported as count and percentage. No statistical testing for baseline characteristics will be reported.

Please refer to the Data Analysis Plan for more details.

Interim analysis

Every month, an interim analysis will be conducted for each study site and of the combined dataset. Interim analyses will start after the 200th participant has been recruited across the two sites. The primary endpoint will be analysed as described above. The Bayesian model yields a posterior distribution of the relative risk (RR). The posterior probability of the superiority hypothesis ($RR < 1$) will be calculated. If during any of the interim analyses, the posterior probability of superiority is > 0.995 , a conclusion is reached, and the trial will be stopped.

Monthly, the following secondary endpoints will be reported from the sites: hospital admissions, and deaths.

IMPLEMENTATION

Inception

The study will begin with an inception meeting to be held in Cape Verde or virtually, depending on travel and quarantine recommendations at the time. Besides administrative issues, the meeting will address:

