Other Outcomes Measures: Hospitalisation for COVID-19; hospitalisation for respiratory infections; COVID-19 infection episodes; Furthermore, we will study the effect on Death for any reason, Death due to documented COVID infection. Cumulative incidence of infectious disease episodes, in particular respiratory infections. Cumulative incidence of infectious hospital admissions, in particular respiratory infections. Cumulative incidence of hospital admission due to documented COVID-19. Cumulative incidence of all-cause and infectious intensive care admission. Cumulative incidence of intensive care admission due to documented COVID infection.

Baseline data collection

Enrolment data regarding chronic illnesses and treatment, lifestyle (family structure, socioeconomic factors, smoking), vaccination history including previous BCG vaccination. Blood sample for SARS-CoV-2 serology.

Follow-up

Follow-up will last for 6 months (182 days). Telephone interviews every second week, regarding symptoms, absenteeism and causes, COVID-19 testing (if done) and their results. Supplemented by daily workplace presence registry information (where present).

End of follow-up

At the end of follow-up, participants will be invited back to the room of the healthcare facility where they were recruited to have another SARS-COV-2 antibody test and to complete the final questionnaire; also, at this time, the research officer will be asked to inspect and report how scarification is in the deltoid area of the right upper limb of the HCW, which may occur due to the BCG vaccine. Information regarding the treatment (BCG or placebo) will be disclosed to the participant at this time.

Sample size

The sample size was calculated on the basis of the primary hypothesis. A total of 1050 HCW randomized with an estimated loss to follow-up of 5%, and a mean number of days off work due to illness in the control group of 5 days (SD=5) over a 6-month period will demonstrate a reduction among BCG vaccinated of 20% for a mean absence of 4 days (80% power and alpha 0.05). The estimated loss to follow-up (5%) was based on past telephone-based surveys conducted in Bissau.

Statistical analysis.

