Absenteeism besides COVID-19	Refers to the number of days absent from work due to illness besides COVID-19	Quantitative	Numeric	In days
Absenteeism for infections	Refers to the number of days (unplanned) absent from work due to infections	Quantitative	Numeric	In days
Absenteeism for respiratory infections	Refers to the number of days (unplanned) absent from work due to respiratory infections	Quantitative	Numeric	In days
COVID-19 infection	Describes if the participant is positive for SARS-CoV2 or has had COVID-19	Qualitative	Nominal	No Yes
Death	Whether the participant died during follow-up	Qualitative	Nominal	No Yes
Cumulative incidence of infectious disease episodes	Cumulative incidence of infectious disease episodes	Quantitative	Numeric	Episodes
Cumulative incidence of respiratory infectious disease episodes	Cumulative incidence of respiratory infectious disease episodes	Quantitative	Numeric	Episodes
Cumulative incidence of hospital admissions	Cumulative incidence of hospital admissions	Quantitative	Numeric	Admissions
Cumulative incidence of infectious disease hospital admissions	Cumulative incidence of infectious hospital admissions	Quantitative	Numeric	Admissions

Variable	Definition	Type	Scale	Domain
Cumulative incidence of respiratory infectious hospital admissions	Cumulative incidence of respiratory infectious hospital admissions	Quantitative	Numeric	Admissions
Cumulative incidence of hospital admissions due to documented COVID-19	Cumulative incidence of hospital admissions due to documented COVID-19	Quantitative	Numeric	Admissions
Cumulative incidence all-cause and infectious intensive care admission	Cumulative incidence all-cause and infectious intensive care admission	Quantitative	Numeric	Nights
Cumulative incidence of intensive care admission due to documented COVID-19 infection	Cumulative incidence all-cause and infectious intensive care admission	Quantitative	Numeric	Nights

6. General Statistical considerations

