Primarily a descriptive analysis will be performed of all information contained in the two study groups (BCG and placebo). All variables will be analysed, one by one, to know their distribution. Background factors will be summarised by counts (percentages), means (standard deviation) or medians (interquartile range) as appropriate. Proportions will be compared using the chi-square test - χ^2 test or Fisher's Exact test (categorical variable) or Student's t-test or Mann-Whitney test (quantitative variable) according to the distribution of variables. Statistical significance was set at the 5% level (two-tailed tests) and 95% confidence intervals (95%CI) for the estimates.

The endpoints variables (table 1) will be analyzed using univariate analysis (Logrank test) and Multivariate analysis (Cox Proportional Hazard Regression, or Cox Regression), stratified by the block randomization variables gender (male/female) and occupational group (doctors/ nurses/other) in addition to site. Covariates will be tested in the model univariate, and only those that were associated with the outcome at a significance level of at least 20% will be retained in a possible multivariate model. A significance level (p-value) of less than 0.05 and its respective confidence intervals (CI) will be used.

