For the univariate analysis to check the difference between the BCG versus Placebo groups we will use the Logrank test of significance by means of its p-value or confidence interval. For the univariate analysis to check the difference between the BCG versus Placebo groups we will use the Logrank test of significance by means of its p-value or confidence interval. In the multivariate analysis for the comparison of the two analyzed groups, we will use the Cox Proportional Hazard Regression, or Cox Regression. This allows us to obtain results adjusted for possible confounding variables. Cumulative incidence data will be analysed in Cox proportional hazards models. The Cox Model, which is semi-parametric, assumes that failure rates are proportional, that is, the risk of failure of the variables is constant over time. Survival analysis will allow us to correctly assess the rate at which events (outcomes) are occurring in the different groups in our study.

7. Demographics and other baseline characteristics

Baseline characteristics

Table 2 – Baseline characteristics of the participants

Variable	Type	BCG vaccine	Placebo	Statistical (P-value)
Age (years)	Quantitative	$\bar{X} \pm SD$ or Md (IQR)	$\bar{X} \pm SD$ or Md (IQR)	Student's t-test or Mann-Whitney test
Gender				
Female	Categorical	% (n/N)	% (n/N)	χ^2 test or Fisher's exact test (P-value)
Male		% (n/N)	% (n/N)	
Number adults (> 18 years) living in the household	Quantitative	$\bar{X} \pm SD$ or Md (IQR)	$\bar{X} \pm SD$ or Md (IQR)	Student's t-test or Mann-Whitney test
Adult living at home and also healthcare worker	Quantitative	$\bar{X} \pm SD$ or Md (IQR)	$\bar{X} \pm SD$ or Md (IQR)	Student's t-test or Mann-Whitney test
Number children (<18 years) living in the household	Quantitative	$\bar{X} \pm SD$ or Md (IQR)	$\bar{X} \pm SD$ or Md (IQR)	Student's t-test or Mann-Whitney test
Age of the youngest child living in the household (years)	Quantitative	$\bar{X} \pm SD$ or Md (IQR)	$\bar{X} \pm SD$ or Md (IQR)	Student's t-test or Mann-Whitney test
Animals living in the household				
Dogs	Categorical	% (n/N)	% (n/N)	χ^2 test or Fisher's exact test (P-value)
Cats		% (n/N)	% (n/N)	
Pigs		% (n/N)	% (n/N)	

Variable	Type	BCG vaccine	Placebo	Statistical (P-value)	
Birds		% (n/N)	% (n/N)		
Sheep		% (n/N)	% (n/N)		
Other		% (n/N)	% (n/N)		
Person living in the household diagnosed with COVID-19					
No	Categorical	% (n/N)	% (n/N)	χ^2 test or Fisher's exact test (P-value)	
Yes		% (n/N)	% (n/N)		
Occupation					

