Suspected but not confirmed				
No		% (n/N)	% (n/N)	χ^2 test or Fisher's exact test (P-value)
Yes	Categorical	% (n/N)	% (n/N)	
COVID test in the last 2 weeks				
No		% (n/N)	% (n/N)	χ^2 test or Fisher's exact test (P-value)
Yes	Categorical	% (n/N)	% (n/N)	
COVID test type				
RT-PCR (swab in the throat or nose)		% (n/N)	% (n/N)	χ^2 test or Fisher's exact test (P-value)
Rapid test for the antibodies detection in the blood (finger prick)		% (n/N)	% (n/N)	
	Categorical			
RT-PCR result				
Positive		% (n/N)	% (n/N)	χ^2 test or Fisher's exact test (P-value)
Negative		% (n/N)	% (n/N)	
Missing		% (n/N)	% (n/N)	
Rapid test result				
Positive		% (n/N)	% (n/N)	χ^2 test or Fisher's exact test (P-value)
Negative		% (n/N)	% (n/N)	
Missing		% (n/N)	% (n/N)	

8. Analysis of endpoints

Table 4 – Analysis of endpoints from Bayesian analysis

Endpoint Variable	BCG	Placebo	Risk Ratio (95%CI) p-value
Absenteeism	$\bar{X} \pm SD$ or Md (IQR)	$\bar{X} \pm SD$ or Md (IQR)	RR (95%CI) p-Value
Absenteeism for COVID-19	$\bar{X} \pm SD$ or Md (IQR)	$\bar{X} \pm SD$ or Md (IQR)	RR (95%CI) p-Value
Absenteeism besides COVID-19	$\bar{X} \pm SD$ or Md (IQR)	$\bar{X} \pm SD$ or Md (IQR)	RR (95%CI) p-Value
Absenteeism for infections	$\bar{X} \pm SD$ or Md (IQR)	$\bar{X} \pm SD$ or Md (IQR)	RR (95%CI) p-Value
Absenteeism for respiratory infections	$\bar{X} \pm SD$ or Md (IQR)	$\bar{X} \pm SD$ or Md (IQR)	RR (95%CI) p-Value

Table 5 – Analysis of endpoints from Cox regression and Poisson regression

Endpoint Variable	BCG	Placebo	Hazard Ratio (95%CI) p-value
Cumulative incidence of infectious disease episodes	rate (events / risk time)	rate (events / risk time)	HR (95%CI) p-Value
Cumulative incidence of respiratory infectious disease episodes	rate (events / risk time)	rate (events / risk time)	HR (95%CI) p-Value
Cumulative incidence of hospital admissions	rate (events / risk time)	rate (events / risk time)	HR (95%CI) p-Value
Cumulative incidence of infectious disease hospital admissions	rate (events / risk time)	rate (events / risk time)	HR (95%CI) p-Value
Cumulative incidence of respiratory infectious hospital admissions	rate (events / risk time)	rate (events / risk time)	HR (95%CI) p-Value
Cumulative incidence of hospital admissions due to documented COVID-19	rate (events / risk time)	rate (events / risk time)	HR (95%CI) p-Value
Cumulative incidence all-cause and infectious intensive care admission	rate (events / risk time)	rate (events / risk time)	HR (95%CI) p-Value

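### Infectious and respiratory episodes are defined as counts but analysed by ordinary Cox regression, which ignores repeats; separately, the ICU rows of SAP Table 1 need correcting

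*SAP*

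**What the plan says.** SAP section 5, Table 1 lists "Cumulative incidence of infectious disease episodes" and the matching respiratory row as quantitative, numeric variables in the unit *Episodes*. The definition column only repeats the label. Hospital admissions are typed the same way, in *Admissions*. The protocol's Table 1 has the same entries.

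For the model, SAP 6.4 states "Cumulative incidence data will be analysed in Cox proportional hazards models", with a logrank test as the univariate comparison. The protocol's Data analysis section agrees: "Cumulative incidence outcomes will primarily be analysed using Cox Proportional Hazard Regression". SAP 6.4 explains the hazard ratio in terms of a participant still free of the outcome event. SAP section 8, Table 5 shows each arm as "rate (events / risk time" beside a hazard ratio. Neither document states first or all events endpoint by endpoint, or when a new episode begins.

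In Table 1 the row for ICU admission due to documented COVID-19 is defined as "Cumulative incidence all-cause and infectious intensive care admission", the same words as the row above it. Both ICU rows have the unit *Nights*. SAP 9.1 defines ICU admission as an event lasting at least one night.

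**The concern.** Interviews every second week for 182 days can record several infections in one person, and Table 1 asks for their number. A first-event Cox model stops at the first. Later episodes do not enter the estimate, and the hazard ratio answers a different question from the effect on the number of episodes. If people differ in susceptibility, the first-event hazard ratio also lies closer to 1 than the rate ratio. At stake are power and interpretation for two endpoints that bear directly on the SAP's hypothesis of protection against COVID-19 and other infections.

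The ICU entries are a separate matter. Followed literally, the COVID-19 row would count the same admissions as the row above, in a unit that does not match the planned analysis.

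**Working it through.** **The plan's own figures.** No rate, event count or power is given for these endpoints. The only design calculation ("80% power and alpha 0.05", with "a mean number of days off work due to illness in the control group of 5 days (SD=5) over a 6-month period") concerns absence days. A difference of 1 day with SD 5 at two-sided 5% needs 393 per arm, 786 in total, and 786/0.95 = 828 with loss. The planned 1050 is larger and does not bear on this point. It is used here only for the number analysed.

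**Inputs.**
- Analysed: 1050 × 0.95 = 997.5, about 998, so n = 499 per arm.
- Level: two-sided 5% (SAP 6.1: "Statistical significance was set at the 5% level (two-tailed tests").
- Rate ratio 0.80: assumed, by analogy with the 20% reduction hypothesised for absenteeism.
- Control mean m over six months: assumed 0.1, 0.3, 1 and 2.
- Between-person variation: assumed, either none (θ = 0) or gamma frailty with shape k = 1.25, variance θ = 1/1.25 = 0.8.

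**Rate analysis.** Var(log RR) = [1/m + 1/(0.8m) + 2θ]/n, and |log 0.80| = 0.2231. At m = 1:
- θ = 0: 2.25/499 gives SE 0.0671; 0.2231/0.0671 − 1.96 = 1.36; power 91%.
- θ = 0.8: 3.85/499 gives SE 0.0878; 0.2231/0.0878 − 1.96 = 0.58; power 72%.

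**First-event Cox.** The probability of no episode is S(m) = exp(−m), or (1 + θm)^(−1/θ) with frailty. At m = 1:
- θ = 0: expected first events are 499 × 0.632 = 315.4 and 499 × 0.551 = 274.8; SE = √(1/315.4 + 1/274.8) = 0.0825; 0.2231/0.0825 − 1.96 = 0.74; power 77% (simulation 76%).
- θ = 0.8: the cumulative hazard ratio at six months is ln 1.64 / ln 1.80 = 0.842, not 0.80, and its log is −0.172. First events are 259.7 and 230.1; SE 0.0905; 0.172/0.0905 − 1.96 = −0.06; power about 48% (simulation 50%).

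**Power by simulation, rate ratio 0.80.**

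| m | First-event Cox, frailty / none | Rate analysis, frailty / none |
|---|---|---|
| 0.3 | 32% / 39% | 38% / 44% |
| 1 | 50% / 76% | 72% / 91% |
| 2 | 55% / 90% | 86% / 99% |

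At m = 0.1 the two methods are practically equal (17% against 17–18%).

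**Episodes used.** With frailty at m = 1, the first-event share over both arms is (0.520 + 0.461)/(1 + 0.8) = 55%. For rare events, at m = 0.02, a first-event analysis drops only 1–3% of events for frailty variances from 0 to 2.

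**ICU rows.** No arithmetic is needed. The COVID-19 row's label, its Table 5 label and the SAP's outcome list all say documented COVID-19; its Table 1 definition says all-cause and infectious. Table 5 divides events by time at risk and SAP 9.1 defines an admission event; Table 1 gives nights for both rows. The other ICU row joins all-cause and infectious admission, which are two endpoints.

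**The case against.** The best defence is that the plan already describes a first-event analysis. SAP 6.4 places the hazard ratio beside Kaplan–Meier and logrank and describes a risk set of people without the event. The term cumulative incidence fits that, and ordinary Cox is then valid. Events over time at risk is also a normal display for first events with time cut at the event, so Table 5 does not prove that all episodes are meant. First-event analysis is less exposed to counting one illness twice when it spans two interviews. Infectious and respiratory episodes are listed among other outcomes, below the primary and secondary ones. All of this stands. It does not remove the mismatch with the count in Table 1 or the loss of information.

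Two stronger readings do not hold. A reader might infer that the plan produces intervals that are too narrow. That would require repeat episodes to be pooled without clustered variance, together with variation between people. The plan nowhere says that repeats will be pooled, and robust variance being named only for the two Poisson rows does not show it.

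A reader might also take k = 1.25 as implied by the absenteeism mean and SD. Solving 25 = 5 + 25/k does give 1.25, but for days, not episodes. Poisson episodes with mean 1, each lasting exactly 5 days, also give mean 5 and variance 25 × 1 = 25, hence SD 5, with no frailty at all. The value is therefore only one end of an assumed range.

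On the ICU rows, the labels show what was intended, so this looks like a copying slip. The wrong definition affects only the COVID-19 row; the wrong unit affects both.

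**Conclusion.** The point holds for infectious and respiratory episodes: a valid test, but one that ignores repeats and does not estimate the effect on the count that Table 1 defines. Under the assumptions above, the power lost is about 5–6 percentage points at 0.3 episodes per person (44 − 39 and 38 − 32), 15–22 at one (91 − 76 and 72 − 50) and 9–31 at two (99 − 90 and 86 − 55). These figures rest on an assumed rate ratio, episode rate and frailty, none of which the documents give for episodes. For hospital and ICU admissions the loss is negligible if they are rare. The primary endpoint has its own model and is not affected.

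The ICU defect rests on no assumption. One definition and two units in Table 1 contradict other parts of the SAP.

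**What to change.** - **Episode endpoints.** Analyse infectious and respiratory episode counts with negative binomial regression and log(days at risk) as offset, or with Andersen–Gill and participant-robust variance. Report a rate ratio in Table 5 and keep first-event Cox as supportive.
- **Admissions.** Keep Cox and state that it is time to first admission.
- **Table 1, ICU rows.** Define the COVID-19 row as ICU admission due to documented COVID-19, set the unit of both rows to Admissions, and split all-cause from infectious ICU admission. Make the same corrections in the protocol's Table 1.

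The cost is SAP wording and the matching protocol table. Negative binomial regression is already planned for absenteeism, although the offset is new. The real downside is that a rule must be written for when a new episode starts, because one illness can span two biweekly interviews. It should be fixed before the allocation is unblinded.

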Data will be reported quantitatively. All analyses will be performed from the intention-to-treat principle. Missing data on background variables will be dealt with by multiple imputation. Final data analysis will begin when the last participant in the multicentric RCT has completed the follow-up period. The primary endpoint, work absenteeism due to illness, will be reported as the total number of sick days with standard deviation. Continuous baseline characteristics will be reported as means with the standard deviation or medians with the inter-quartile range, as appropriate. Categorical baseline characteristics will be reported as count and percentage. Statistical testing for baseline characteristics will be performed. Days of absenteeism will be analysed using a Bayesian negative binomial regression with a fixed effect for BCG, hospital, professional category, age, enrolment week and number of average workdays per week. Incidence data will be analysed in Cox proportional hazards models. Monthly, data on absenteeism by randomization group will be reported to the DSMB.

Trial registration

The trial is registered at clinicaltrials.gov. (<https://clinicaltrials.gov/ct2/show/NCT04641858>)

Funding

EDCTP is funding the run-in costs for the BCG-COVID-RCT, including trials in the respective countries and for training and management.

Study management, monitoring and quality control

The project is led by an International Steering Committee (ISC) consisting of PIs in each of the five countries involved: [name] (international coordinator), PI from Denmark; [name], PI from Guinea-Bissau; [name], PI from Portugal; [name], PI from Cape Verde; and [name], PI from Mozambique. The overall coordination is the responsibility of the Danish partner. The leader has extensive leadership experience from running a Center of Excellence in Denmark and the research group of the Bandim Health Project in Bissau for many years. The Bandim Health Project has a history of past collaboration with the Portuguese partner. The research group will hold teleconferences at least once a week with a formal pre-established agenda on training, enrollment, follow-up, losses to follow-up, staff turnover, vaccine logistics, quality control of data collection, data entry and database management, interim analysis, communication and dissemination activities, other risks. Decisions from each meeting are recorded by the coordinator.

2. Definitions

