2.2. Analyzed populations

The clinical trial participants are 1,050 HCW (definition below) recruited from hospitals in two different African countries.

The Guinea-Bissau arm of the BCG-COVID-RCT study is conducted in Bissau, the country capital, by the Bandim Health Project (BHP). The team is led by [name]. Inclusions commenced in Guinea-Bissau on December 3rd, 2020, in the Hospital Nacional Simão Mendes. After concluding inclusions at Simão Mendes, inclusions were commenced at other hospitals and health centers.

In Mozambique, this study is being conducted at Manhiça District Hospital (MDH) and Mavalane General Hospital (MGH) by the Centro de Investigação em Saúde de Manhiça (CISM) through the team led by [name]. Manhiça District Hospital is located on the main National Road One, in the capital of the Manhiça district, Maputo Province, southern Mozambique. Manhiça is a rural area located approximately 80km away from the capital, Maputo city; has a total population close to two hundred thousand people. MDH is the referral hospital with more than 100 beds and absorbs the largest proportion of HCW within the district. MGH (260 beds) is located in the district of neighborhood of Mavalane, in Maputo city (Southern Mozambique). The MGH is part of the three general hospitals of the city of Maputo. The health

area of Mavalane is the largest in the city and serves an estimated population of 609.889 inhabitants, about 50% of the health population of the capital of nation capital.

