6.1. General statistical methodology

The database system for both inclusion procedures and follow-up is REDCap (www.project-redcap.org), and the instruments have been developed by the Institute of Hygiene and Tropical Medicine at NOVA University.

Data entry for both inclusion and follow-up procedures is conducted online using the browser version, which means that no participant data is stored locally and that the study responsible(s) can monitor the data collection in real-time.

The randomization code was developed by the trial statistician, [name]. This code produces an allocation table for all the stratification layers and all the sites, with block sizes varying randomly between 4 and 6 within each individual stratum. The allocation table used for the study has not been seen and is not available to any of the researchers involved in the study and it was implemented by an independent statistician, [name], in Bissau.

From the databases of the trials in Guinea-Bissau and Mozambique, their analysis will be performed by either STATA version 17 software (Stata, College Station, TX) or SPSS version 26.

The combined data analysis will begin when the last participant in the multicentric RCT has completed the follow-up period or after the 182 day of the study and data has been cleaned.

Descriptive statistical techniques (absolute and relative frequency distribution) will be used to analyze the quality of the database through the evaluation of two aspects: completeness (field filling) and consistency (consistency between the categories marked in two related fields). The completeness indicator will be calculated as the proportion of filled fields in relation to the total of records, in percentage. Regarding completeness, the results will be categorized as the percentage of records without filling out as follows: excellent (<10% of records without filling out), regular (11 to 30%) and low (>30% of records without filling out).

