Cumulative incidence of intensive care admission due to documented COVID-19 infection	rate (events / risk time)	rate (events / risk time)	HR (95%CI) p-Value
COVID-19 infection*	% (n/N)	% (n/N)	RR (95%CI)
Death*	% (n/N)	% (n/N)	RR (95%CI)

*Analysed in Poisson regression with robust variance estimation, including stratification variables, i.e. country, profession and sex, providing Risk Ratios (RR).

9. Analysis of exploratory endpoints

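### The COVID-19 infection risk ratio omits hospital, age and enrolment date, which the absenteeism model already uses, and SAP 6.1 sets a different analysis for the same endpoint: a small, avoidable loss of precision

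*SAP*

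**What the plan says.** Three parts of the plan bear on how COVID-19 infection (yes/no) is analysed.

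- **SAP section 8, footnote to Table 5**, which covers the COVID-19 infection and Death rows: "Analysed in Poisson regression with robust variance estimation, including stratification variables, i.e. country, profession and sex, providing Risk Ratios (RR".
- **SAP section 6.1**, on the endpoints of Table 1, which include COVID-19 infection: log-rank and Cox regression, "stratified by the block randomization variables gender (male/female) and occupational group (doctors/ nurses/other) in addition to site". Of further covariates, "only those that were associated with the outcome at a significance level of at least 20% will be retained in a possible multivariate model".
- **Protocol, Statistical methods**: "Similar regression models will be used for secondary endpoints". The model this follows is the absenteeism model. Its covariates, given there and in the SAP (Statistical analysis; section 6.4), are a "fixed effect for BCG, hospital, professional category, age, enrolment week and number of average workdays per week".

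On enrolment, SAP section 2.2 dates the first inclusions in Guinea-Bissau to 3 December 2020 at one hospital and adds: "After concluding inclusions at Simão Mendes, inclusions were commenced at other hospitals and health centers". The Protocol (Ethics) dates national approval in Mozambique to March 2021 and an amendment of the inclusion criteria to June 2021. The SAP exclusion criteria bar people with earlier confirmed COVID-19 only up to the start of COVID-19 vaccination of health care workers.

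**The concern.** Hospital, age and enrolment week are judged worth adjusting for when the outcome is days absent, yet the footnote leaves them out when the outcome is infection. For infection the case for enrolment date is, if anything, stronger. Follow-up is a fixed 182 days from each person's own entry, so people enrolled months apart are exposed to different stretches of the epidemic. Eligibility changed at a calendar point, and COVID-19 vaccination was arriving. Country does not capture this, because hospitals in Bissau opened one after another within the country.

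In a log-link model under 1:1 randomisation, leaving out a prognostic baseline variable does not bias the risk ratio. It forgoes precision. At stake is the width of the interval for the outcome that most directly measures the secondary objective on how many workers develop COVID-19. A second problem is that sections 6.1 and 8 prescribe different models and covariates for this row, so the analyst would have to choose between them.

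**Working it through.** **The plan's own figure.** There is none to reproduce. The documents give no infection risk, power or target interval width for this endpoint. The sample-size statement concerns absenteeism only.

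**Inputs.** From the SAP: 1050 randomised, 5% loss, so 1050 × 0.95 ≈ 998, or 499 per arm. Assumed: a true RR of 0.8, the control risk p, and the coefficient of variation (cv) of individual risk that the added covariates explain.

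**Width of the planned interval.** SE(log RR) = √[(1−p)/(499p) + (1−0.8p)/(499×0.8p)].

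- p = 10%: SE 0.203, interval around RR 0.8 of 0.54 to 1.19.
- p = 30%: SE 0.105, interval 0.65 to 0.98.

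**Effect of adding covariates, by formula.** The SE is multiplied by about √(1−R²), with R² = p·cv²/(1−p).

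| p | cv 0.5 | cv 0.75 | cv 1.0 |
|---|---|---|---|
| 5% | 0.993 | 0.985 | 0.973 |
| 10% | 0.986 | 0.968 | 0.943 |
| 20% | 0.968 | 0.927 | 0.866 |
| 30% | 0.945 | 0.871 | 0.756 |

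For example, p = 10% and cv = 0.5 give R² = 0.1×0.25/0.9 = 0.028 and √0.972 = 0.986. The formula applies the control risk to both arms and treats covariate effects as known, so it flatters the gain somewhat.

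**Simulation A: hospital, age and four-week enrolment period added.** N = 998, robust Poisson, 400 trials per setting. Entries are the mean ratio of the adjusted to the planned SE.

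| p | no covariate effect | moderate (log-risk SD about 0.43) | strong (0.87) |
|---|---|---|---|
| 3% | 1.001 | 1.003 | 0.991 |
| 10% | 1.002 | 0.992 | 0.964 |
| 30% | 1.001 | 0.966 | 0.877 |

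At p = 3% the fuller model gave the larger SE in 40-53% of trials. In the bottom-right cell the empirical SD of the estimates fell less than the reported SE (ratio 0.929). A repeat of three of these settings (10% strong, 30% moderate and strong) with more trials gave practically the same SE ratios and close to nominal coverage under both models.

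**Simulation B: enrolment period only.** N = 1050, blocks of 4 or 6 within sex, occupation and country, four periods (Guinea-Bissau in all four, Mozambique in the last three), 1500 trials per scenario. The SE reduction is 1 − 1/ratio.

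| Six-month risk by period | planned SE / adjusted SE | SE reduction |
|---|---|---|
| flat 25% | 1.001 | 0.1% |
| 15-30% | 1.007 | 0.7% |
| 10-40% | 1.022 | 2.2% |
| 10-50% | 1.040 | 3.8% |
| alternating 40/10% | 1.059 | 5.6% |
| alternating 50/10% | 1.097 | 8.8% |

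The mean estimate was the same under both models. In the last row the planned variance is 1.097² ≈ 1.20 times the adjusted one, and power is 0.52 instead of 0.59.

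**Hand check at low risk.** Alternating 8% and 2% has mean 5% and variance 0.03² = 0.0009. Then R² = 0.0009/(0.05×0.95) = 0.019, and the planned SE is about 1% larger.

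**In interval terms.** At p = 10% with strong covariates, 0.203 × 0.964 = 0.196, so 0.54-1.19 becomes about 0.55-1.17. At p = 30%, 0.105 × 0.877 = 0.092, so 0.65-0.98 becomes about 0.67-0.96.

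**The case against.** The best defence is that nothing in the footnote is an error. Adjusting for the stratification variables is a standard choice, the estimate is unbiased and the interval is valid. That stands. A reader might infer that the interval is plainly too wide, or wrong. The documents do not support that, because the loss depends on an infection risk and a covariate strength that they never state. With low or flat risk the loss is nil.

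Second, section 6.1 already brings in site and possibly more, so it would be unfair to say that infection is adjusted for three variables and nothing else. That is a fair qualification, but it does not settle the matter. The footnote is the rule written for this row, and it uses a different model. The screen in section 6.1 picks covariates from the outcome data. Site may also mean country, as it does in SAP section 3, and would then add no hospital adjustment.

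Third, allocation runs in small blocks from a table that covers "This code produces an allocation table for all the stratification layers and all the sites". The arms are therefore roughly balanced over enrolment time, and part of the gain is a reported SE that comes down to its true value rather than a more stable estimate. That stands, but the reader still gets a narrower valid interval.

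Fourth, one might call hospital, age and enrolment date the strongest predictors available. The documents do not show this. Baseline antibodies, care of COVID-19 patients and COVID-19 vaccination are also recorded, and no prognostic strength is given for any variable. Nor is the endpoint clearly confined to new infections: SAP Table 1 says it "Describes if the participant is positive for SARS-CoV2 or has had COVID-19".

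Last, the SAP places infection episodes among other outcome measures, and the Protocol treats the antibody testing as not central to the main objective. This limits the weight of the point.

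**Conclusion.** The concern holds as an efficiency point. The footnote omits baseline variables that the trial already collects and uses elsewhere, and staggered enrolment gives good reason to expect at least enrolment date and hospital to predict infection. The interval is likely wider than necessary.

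In simulation the reduction in SE is about 0-4% at infection risks up to 10%. The formula reaches 5.7% at 10% risk only with a cv of 1.0. The reduction is about 6-12% only when infection is common and varies strongly with enrolment date or the other covariates. Common infection alone is not enough: moderate covariates at 30% risk give 3.4%. All of this rests on assumed risks, covariate strengths and RR 0.8. Simulation B covers enrolment period alone, and simulation A does not separate the shares of hospital and age.

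The mismatch between SAP sections 6.1 and 8 needs no assumption and should be resolved in any case. Severity: minor.

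**What to change.** Amend the footnote to SAP Table 5 before infection data are compared by arm:

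- For the COVID-19 infection row, keep Poisson regression with robust variance and adjust for hospital (in place of country), profession, sex, age and coarse enrolment date. Enrolment date can enter as calendar month or as a spline with about 4 degrees of freedom.
- State that this replaces the Cox model and the 20% univariate screen of section 6.1 for this endpoint.
- Leave the Death row as it is. It shares the footnote, and with few deaths extra hospital and time terms would be unsafe.

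The cost is one SAP edit and no new data, since every variable is already in the absenteeism model. The downside is a few more model parameters, with negligible gain if infections turn out to be few. In that case the spline is preferable to monthly indicators.
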